10.7 Software

TrialOnline will be used for DM.

# 11 QUALITY CONTROL AND QUALITY ASSURANCE

The principles of GCP are followed throughout the study. During the PET scans, the SOPs of are followed and for DM and statistics, the SOPs of are followed.

quality certificates will be available prior to study initiation and will be filed in the ISF and TMF.

The study will be monitored by The study monitor is allowed to monitor the study as frequently as necessary to ensure that data recording and protocol adherence are satisfactory. The CRFs and related source data will be reviewed in detail and source data verification will be performed according to the monitoring plan.

The quality assurance personnel and the Sponsor may conduct audits in any phase of the study. The study may also be inspected by CAs.

A curriculum vitae in English will be obtained from all investigators who sign the protocol and from other relevant persons.

Laboratory

# 12 ETHICAL CONSIDERATIONS

This study will follow the relevant regulations and guidance for biomedical research involving human subjects, such as the Declaration of Helsinki, GCP, national laws and EU directives. Special emphasis will be put on the well-being of the study subjects.

Prior to initiation of the study, the study protocol, the subject information leaflet and the ICF, the Description of the Study Data Register and the texts of any advertisements used for the recruitment of study subjects will be submitted to and approved by an independent EC. The EC will also be notified of any other materials to be given to the subjects (*e.g.* study subject diary, participant card). The study will be authorized by the CA (the Finnish Medicines Agency, Fimea) before its commencement.

The study subject candidates will be provided with both verbal and written information on the study, its risks and benefits. They are encouraged to ask questions on the study. After having had enough time to consider their participation, they may sign the IC form. No study procedure will be implemented prior to obtaining written IC that is signed by the subject at the time of consent. A copy of the signed ICF will be given to the subject. The investigator will keep each subject's signed ICF on file for inspection by a regulatory authority at any time.

The subjects are told what information will be collected of them and how. The collection of study data and its confidential storage are described in the Description of the Personal Data Register, which is kept in the ISF and is available for inspection by the subjects. The investigator assures that the privacy of the subjects, including their personal identity and all medical information, will be maintained at all times.

This study involves exposure to ionizing radiation, which is harmful to living organisms. The total radiation dose from two up to 500 MBq C-acetate PET tracer injections and low-dose CT scans for attenuation correction will be 7.5 mSv. The average annual radiation dose of a person living in Finland derived from the environment and from medical uses of radiation is approximately 3.2 mSv per year (Radiation and Nuclear Safety Authority of Finland). Therefore, the radiation exposure from this study will be approximately equivalent to 2 years and 4 months of background radiation in Finland. Despite the ionizing radiation exposure being low, any radiation dose may increase the risk of cancer.

Other invasive procedures included in the study are the frequent blood samplings. The volume of blood drawn from each subject during the scheduled visits will not exceed 50 ml. This blood loss should not produce any adverse effects. Echocardiography is a non-invasive ultrasound-based imaging method used to assess cardiac function that is not associated with any known safety risks.

The subjects are urged to report all AEs to the study personnel and they are given the phone numbers of the investigator and study nurse(s) whom they are instructed to call if they observe significant, possibly study drug related AEs, or in other urgent study-related issues.

The subjects included to this study will have chronic HF, NYHA II-III symptoms and reduced EF. Their ongoing HF treatment will not be modified, with the exception of

changing their ACEI or ARB medication to valsartan during the screening/run-in period. The medication change and subsequent possible up-titration will be closely monitored by the study team to ensure subject safety at all times. During the doubleblind treatment period, subjects will receive either sacubitril/valsartan or valsartan and are expected to remain in a stable clinical condition. Also during this period, possible up-titration(s) will be closely monitored by the study team. In addition to the above mentioned medication changes, the study protocol allows for down-titration of a loop diuretic, if indicated based on clinical signs and/or symptoms. This study is designed so that the health and safety of the subjects can be monitored as closely as possible.

Substantial changes to the final approved study protocol will be initiated only with the EC's favorable opinion of a written amendment, except when necessary to eliminate immediate hazards to the study subjects. When a change involves only logistics or administration, it will be considered non-substantial, and needs not be submitted to the EC or the CA for approval. The CA will also be notified before adopting a substantial amendment.

After the study has been completed and a Clinical Study Report prepared, the EC and CA will be notified as agreed by the Sponsor **Complete and**.

# 13 DATA HANDLING AND RECORD KEEPING

### 13.1 Case report forms

Data to be collected according to the study protocol (and its amendments, if any) shall be recorded on study-specific eCRFs generated by The data will be recorded with electronic data capture (EDC) using eCRFs at the study center. All data on the CRFs must be verifiable in the source data unless declared as source data in the monitoring plan.

CRFs are required for each study subject. They will be completed in English by the investigator or other authorized study personnel. The investigator has to confirm the content of the CRF by an electronic signature.

Corrections to the CRFs may be made by the investigator or other authorized study personnel. An audit trail within the system will track all changes/corrections made.

Instructions and training for completing the CRFs will be provided. These instructions will cover the content and technical issues of the EDC system.

### 13.2 Source data

Source data will recorded in the study subject's medical records. Access to the source data revealing the identity of the study subjects is only to the study personnel and study monitor. The generated source data are stored at

The laboratory results of the blood safety determinations and biomarkers are stored as print-outs within the ISF and in the patient records of

the personnel of which is bound to professional secrecy.

### 13.3 Deviations

In case the study monitor, the investigator, a study nurse or other authorized person involved in the study observes a protocol deviation or discrepancy, he/she should describe the issue as clearly as possible in a written memorandum. In addition to the date and signature of the writer, the investigator, the monitor or an authorized Sponsor's representative will also sign the memorandum. Deviations concerning a single subject will be described in the corresponding CRF.

### 13.4 Amendments

Minor changes (*e.g.*, concerning logistics or administration) to the clinical study protocol can be clarified in a memorandum or in a non-substantial amendment, if the change has no effect on the safety of the subjects or on the scientific value of the study. The investigator will inform the Sponsor of such minor changes. All essential changes to the clinical study protocol are described in a substantial amendment, which is submitted for approval by the EC and CA before adopting the changes, except when necessary to eliminate immediate hazards to the study subjects. Amendments to the clinical study protocol are prepared as agreed by the parties involved in the study.

# 14 STUDY SCHEDULE

The study is planned to be carried out Q3/2017 - Q2/2019.

# 15 CRITERIA FOR PREMATURE STUDY TERMINATION

The study may be discontinued at the clinical site at the discretion of the Principal Investigator and/or the Sponsor based *e.g.* on the occurrence of the following:

- ADRs unexpected to date in respect to their nature, severity, and duration or the unexpected incidence or severity of expected ADRs.
- Medical or ethical reasons affecting the continued performance of the study.
- Difficulties in the recruitment of subjects.
- Significant deviations from the protocol.

The investigator will inform the EC and the sponsor will inform the CA if the study is terminated prematurely. The Sponsor reserves the right to prematurely terminate the study for valid scientific or administrative reasons. In the case of premature termination of the study, the investigator will proceed to appropriate actions (described in a separate memorandum) concerning the study subjects.

# 16 FINANCING AND INSURANCE

Financial matters related to the study are covered by an agreement between the Sponsor, and in appropriate agreements between any other relevant parties of the study. The Sponsor has an insurance policy covering damages caused by the investigational products administered during the study. The insurance statement will be provided in the ISF and TMF. In case of any injury caused by an incident that is related to the study procedures but is not causally related to the investigational products, study subjects will be covered by the patient insurance of

# 17 STUDY REPORT AND PUBLISHING

A final Clinical Study Report will be prepared after the study has been completed or prematurely terminated. The Sponsor may submit the report to another party. The EC will be notified by while the CA will be notified by the sponsor about study completion according to applicable laws and regulations. The study report will be approved by the principal investigator and the Sponsor. The Sponsor remains the exclusive owner of the study data defined in the protocol. All involved parties agree that the study results should be published according to usual scientific practice. The eventual publication of the study results and authorship of the eventual publication(s) will be mutually agreed. Manuscripts will not be submitted for publication without prior approval of the Sponsor.

# 18 ARCHIVING

The ISF (including *e.g.* source data, subject screening and identification logs, original signed ICFs, copies of CRFs, and drug accountability records) will be archived by study site to enable possible follow-up assessments or audits by the Sponsor, or inspections by regulatory authorities. The ISF is archived for at least 15 years after the end of the study, unless specified otherwise by a written agreement between the Sponsor and study site. The study site may lend materials of this study to third parties on the Sponsor's documented permission.

The Sponsor will archive the TMF according to applicable laws and regulations. Information collected during the course of this study will be stored by the Sponsor and used in the further development and understanding of the study drug for as long as the information is relevant for patient care. Its use includes the transfer of data to regulatory authorities of the European Union or its member or affiliated states (*i.e.* non-EU countries belonging to the European Economic Area, EEA), the USA or other non-EU/EEA countries for the purpose of obtaining, maintaining and processing of marketing authorizations. All information is handled confidentially and according to the current laws and regulations.

# 20 APPENDICES

Appendix 1. Subject information sheet and Informed consent form Appendix 2. Signed consent of the investigator(s)

# Document History – Changes compared to previous final version of SAP

| Date                | Time
point             | Reason for
update            | Outcome for update | Section and title
impacted
(Current) |
|---------------------|---------------------------|---------------------------------|--------------------|--|
| 2022-
Apr-
25 | Prior
to
DB
lock | Creation of
final
version | NA - First version | NA   |

# List of abbreviations

| AE     | Adverse Event                                  |
|--------|--|
| ACEI   | Angiotensin Converting Enzyme Inhibitor        |
| ARB    | Angiotensin II type - 1 Receptor Blocker       |
| ATC    | Anatomical Therapeutic Chemical                |
| BID    | Twice a Day                                    |
| CRF    | Case Report Form                               |
| CSR    | Clinical Study Report                          |
| DMS    | Document Management System                     |
| DTS    | Data Transfer Specification                    |
| EDC    | Electronic Data Capture                        |
| FAS    | Full Analysis Set                              |
| HF     | Heart Failure                                  |
| HR     | Heart Rate                                     |
| IA     | Interim Analyses                               |
| IMP    | Investigational Medicinal Product              |
| MedDRA | Medical Dictionary for Drug Regulatory Affairs |
| PK     | Pharmacokinetics                               |
| PPS    | Per-Protocol Set                               |
| PRO    | Patient-reported Outcomes                      |
| PT     | Preferred Term                                 |
| RAAS   | renin - angiotensin - aldosterone system       |
| RAP    | Reporting & Analysis Process                   |
| SAE    | Serious Adverse Event                          |
| SAF    | Safety analysis set                            |
| SAP    | Statistical Analysis Plan                      |
| SAS    | Statistical Analysis System                    |
| SOC    | System Organ Class                             |
| TEAE   | Treatment Emergent Adverse Event               |
| TFLs   | Tables, Figures, Listings                      |
| WHO    | World Health Organization                      |

# 1 Introduction

The statistical aspects of this study is briefely described in the protocol. The purpose of this Statistical Analysis Plan (SAP) is ot provide a more detailed description of the analyses to be conducted in this study. This SAP is based on:

- Clinical Study Protocol, Version 3, dated 24 June 2020
- CRF version: \_\_\_\_\_PET\_CR5 (ver 1), dated 21 Sep 2020

# 1.1 Study design

This is a phase IV, prospective, randomized, double-blind, double-dummy, parallel group study, performed at a single center that is formed by . The subjects enrolled into this study are subjects with chronic heart failure (HF) who fulfill all of the inclusion criteria and none of the exclusion criteria.

This study consists of two parts, a screening/run-in period (up to 6 weeks) and a treatment period (approximately 8 weeks). The subjects who sign the ICF entered the screening/run-in period of the study.

During the screening/run-in period the subject will be switched to valsartan treatment and this will replace his/her previously used ACEI or ARB treatment. The starting dose of valsartan will be 80 mg BID or if the dose of previous RAAS blockage medication has been higher, the valsartan dose will be 160 mg BID. Approximately one week after the screening visit 1, screening visit 2 will be scheduled in order to evaluate the safety and efficacy of the ongoing valsartan treatment. Only subjects who tolerate 80 mg BID or 160 mg BID of valsartan and can maintain a stable dose for at least 4 weeks will be eligible to enter into the treatment period.

After the screening evaluations and confirmation of eligibility, the subjects will be randomized into the following two treatment arms in a 1:1 ratio:

- the sacubitril/valsartan treatment arm
  - the valsartan treatment arm

The randomization is generated by an independent statistician at using SAS®.

Study drugs will be dispensed by an unblinded member of the study team during the treatment period while the study personnel directly involved in the clinical assessments will remain blinded throughout the study. The starting dose for each subject in the sacubitril/valsartan arm

| Novartis | Confidential | Page 8 of 30           |
|----------|--------------|------------------------|
| SAP      |              | Study No. CLCZ696BFI03 |

will be 100 mg BID and in the valsartan arm 80 mg BID or 160 mg BID. The study subjects will return to the study center 2-3 times during the treatment period at approximately 2 weeks (visit 1), 3 weeks (visit 2) and 8 weeks (visit 3) after the start of the treatment period.

During visit 1, possible dose up-titration will be considered. Every subject should be attempted to be up-titrated to the next dose level (sacubitril/valsartan 200 mg or valsartan 160 mg, if the latter needed), if clinically possible. If up-titration is not possible, the starting dose should be maintained. After visit 2, if clinically indicated, the dose of the study treatment may be modified (up- or down-titrated) up to week 4.

During the treatment period, the subjects will self-administer two tablets from two study drug packages BID (one tablet from the study drug package containing the active treatment and one tablet from the study drug package containing the placebo). The last study visit will include the final efficacy assessments.

No more than 50% of the study subjects are allowed to have diabetes. To achieve similar groups randomization was stratified by:

- renal insufficiency (GFR 45-60 or >60 mL/min/1.73m^2) and/or
- diabetes mellitus (on insulin or oral glucose-lowering therapy)
- baseline HF therapy (valsartan 160 mg BID at the time of randomization)

The general study design is presented in Figure 1, and the titration patterns according to treatment arms are presented in Figure 2 and 3.

[figure not shown]

Figure 1 Study design

[figure not shown]

Figure 2. Study treatment during the double-blind treatment period with sacubitril/valsartan.

[figure not shown]

Figure 3. Study treatment during the double-blind treatment period with valsartan.

# 1.2 Study objectives, endpoints and estimands

This study was not designed with the estimand framework according to ICH E9(R1) taken into consideration. The primary analysis is based on FAS and the intention is to strive to correspond to a Treatment Policy approach to analysis of data based on this population. However, as intercurrent events may have lead to withdrawal of subjects from the study that would otherwise not have been withdrawn, had the treatment policy estimand framework been taken into consideration, the interpretation of the results may not fully correspond to a treatment policy approach.

## **Primary objective**

The primary objective of the study is to evaluate the effects of 6 weeks of stable sacubitril/valsartan therapy, as compared with valsartan therapy, on the efficiency of cardiac work in subjects with NYHA II-III HF and reduced systolic function using C-acetate and echocardiography.

## Exploratory objectives and endpoints

The exploratory objective of the study is to evaluate the effects of 6 weeks of stable sacubitril/valsartan therapy, as compared with valsartan therapy, on myocardial oxygen consumption and cardiac and systemic hemodynamics.

## 1.2.1 Primary Endpoint

Difference in cardiac efficiency will be evaluated by comparing the results obtained after 6 weeks of stable treatment to the results from the baseline visit.

# 1.2.2 Secondary Endpoints

Difference in the following cardiac and systemic hemodynamic parameters will be evaluated as exploratory endpoints:

- Ejection fraction (EF)
- N-terminal prohormone brain natriuretic peptide (NT-proBNP),
- Systemic BP,
- Systemic vascular resistance (SVR),
- Coronary Cascular Resistance
- Cardiac Oxygen Consumption.

# 2 Statistical methods

# 2.1 Data analysis general information

The statistical analyses in this study will be conducted by the CRO using SAS 9.4M3. At the raw data generated by electronic data capture (EDC) system will be combined to applicable analysis data sets, as required, and statistical output will be generated based on these aggregated data sets.

All data will be tabulated using summary statistics and/or listed. For continuous data both absolute values and the corresponding changes form baseline will be presented, and the following summary statistics will be included; number of observations, mean, standard deviation, minimum, first quartile, median, third quartile and maximum. In addition gemetric mean and coefficient of variation may be provided in the summaries of efficacy endpoints, as applicable.

Categorical data will be presented as counts and percentages, i.e., n (xx.x%). Changes form baseline in categorical data will be displayed in shift tables. Percentages will be based on the number of subjects in the analysis data set used.

Summary statistics will be presented by randomized treatment group and in total, and by visit and assessment time, as applicable. In addition, summary statistics may be presented by final titrated dose group during run-in period and other stratification factor levels as described in the each section of this document.

## 2.1.1 General definitions

| Baseline     | Generally, a baseline measurement refers to the last non-missing
assessment made before the first administration of randomized
treatment (baseline visit). This is valid for, for example, vital signs
and laboratory data, where a difference from baseline is derived.  |
|--------------|--|
| Relative day | The relative day of an event with a start date is derived as:
Relative day = (Start date) - (Baseline date) + 1
For events occurring or starting before baseline the relative day is
derived as:
Relative day = (Start date) - (Baseline date)
In this way, there will be no Day 0. Day 1 is the same day as
baseline, and Day -1 is the day before. |
| Date format  | All dates in analysis datasets and tables, listings and figures will be
in the format YYYY-MM-DD  |

| Treatment
Emergent | All Adverse Events occurring on, or after the day of randomization will be considered Treatment Emergent (TE)   |
|-----------------------|---|
| First drug date       | The first administration of randomized treatment is assumed to be
on the same day as randomization   |
| Last drug date        | The last day of randomized treatment (treatment end date) is stated
on the study termination page in CRF.  |
| By dose level         | In all cases where summaries are stated to be by dose level, then
data will be summarized by the final titrated dose level during the
run-in period, ie the stratification by dose. |

# 2.2 Analysis sets

The following analysis sets will be used for the statistical analysis and presentation of data:

- The safety analysis set (SAF) will consist of all randomised subjects who received at least one dose of the study medication in the treatment period, provided that there was at least one safety follow-up performed for the subject.
- The full analysis set (FAS) will consist of all randomised subjects who have received at least one dose of study medication in the treatment period and have at least one post-baseline assessment of any efficacy endpoints.
- The per protocol set (PPS) will consist of all subjects in the FAS who received at least 75% of the study drug doses, and do not have any other major protocol violations which will affect the assessment of efficacy. Major/important protocol violations may include, but are not limited to, the following:
  - Non-fulfillment of all inclusion criteria
  - o Fulfillment of at least one exclusion criteria
  - Use of certain concomitant medications (this will be judged on a case to case basis, depending on extent of treatment)

The final criteria for PPS, regarding which protocol deviations that warrant exclusions, will be determined when all data on protocol violations/deviations are available and before breaking the blind. The decision of what protocol violations/deviations will lead to exclusion as well as the final classification of subjects according to analysis sets will be documented and signed off before breaking the blind. These decisions will be documented in a separate Pre-Analysis Review document.

The FAS is considered as the primary analysis dataset, and will be used for all primary and secondary efficacy analyses. The primary efficacy analysis will be repeated using the PPS.

| Novartis | Confidential | Page 13 of 30          |
|----------|--------------|------------------------|
| SAP      |              | Study No. CLCZ696BFI03 |

Any significant discrepancy between the results from the FAS and the PPS will be analysed and discussed.

Baseline presentations will be based on the safety set.

Safety presentations will be based on the safety set.

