The total duration of the study is planned to be approximately 14 weeks for each subject, but it may be longer if required for scheduling purposes. During the study, the subjects will have 5-6 study visits. Two of these visits, screening visit 2 and visit 2, may performed as a remote visit (i.e. telephone contact), if deemed sufficient by the investigator. In addition, unscheduled visits may occur at any time, if considered necessary for subject safety. The study includes a screening/run-in period (up to 6 weeks) and a treatment period (approximately 8 weeks). Both the screening/run-in and the treatment period may be longer, if necessary. Efficacy assessments, i.e. C-acetate PET-scan and echocardiography, will be performed twice during the study. The first assessments will be done at the baseline visit, after the subject has been on a stable valsartan treatment for a minimum of 4 weeks, and then repeated at the last visit, when the subject has been on a stable sacubitril/valsartan or valsartan treatment for a minimum of 6 weeks. Subject safety will be monitored throughout the study by evaluating the subject's clinical status, blood pressure (BP), heart rate (HR) and safety laboratory assessments. Specific safety-related withdrawal criteria are given in section 5.8.

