# 8.3.2 Blood pressure and heart rate

BP and HR will be measured in a seated position after at least 5 min rest at all site visits for safety assessment. BP and HR will be monitored also during the imaging sessions according to separate written instructions. SVR will be calculated based on peripheral BP and cardiac output.

In case of abnormal findings, additional control assessments may be performed according to investigator's judgement.

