# 2.4 Analysis supporting primary objective(s)

# 2.4.1 **Primary endpoint(s)**

The primary endpoint is this study is change from baseline in cardiac efficiency at visit 3, after 6 weeks of stable sacubitril/valsartan or valsartan treatment.

The definition of cardiac efficiency is (LV work/gram of tissue) / Oxygen consumption. Where LV work/gram of tissue is obtained by Echocardiography as (SBP x SV x HR) / LV mass, and Oxygen consumption is obtained by Cacetate PET as tracer as a mono exponential clearance rate of Cacetate (kmono)

So, cardiac efficiency is calculated based on the following formula:

Myocardial efficiency = ((SBP x SV x HR)/LV mass)/Kmono

Where

- SBP : Systolic blood pressure during PET
- SV : Stroke volume (Echocardiography)
- HR : Heart rate
- Kmono: Mono-exponential clearance rate (11C-acetate PET- scan)
- LV mass: Left ventricular mass

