# 2.4.4 Handling of missing values not related to intercurrent event

In case of any missing response data for the primary analysis, then the missing data will be imputed using Multiple Imputation (MI). The missing data will be imputed based on the factors (treatment and stratification) and baseline as covariate as applied in the ANCOVA for the primary analysis.

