# 2.5 Analysis supporting secondary objectives

# 2.5.1 Secondary endpoint(s)

The changes in the following cardiac and systemic hemodynamics parameters will be evaluated as exploratory secondary efficacy endpoints:

- Ejection fraction (EF)
- N-terminal prohormone brain natriuretic peptide (NT-proBNP)
- Systemic BP, evaluated in relation to PET and Echocardiography
- Systemic vascular resistance (SVR)
- Coronary Vascular Resistance
- Cardiac Oxygen Consumption (kmono)

Systemic vascular resistance (SVR) will be derived as SBP/( SV x HR) and Coronary Vascular Resistance will be derived as SBP/myocardial perfusion (measured from acetate scan using K1).

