# 2.10 Biomarkers

Biomarkers will be measured to understand the potential mechanisms of how sacubitril/valsartan changes myocardial efficiency. Blood samples will be obtained for measurement of NT-proBNP hs-troponin and creatinine to assess effects of interventions on hemodynamics before randomization and repeatedly on visit 3, after 6 weeks of stable sacubitril/valsartan or valsartan treatment.

These biomarkers will be summarized using descriptive statistics including levels at baseline and Visit 3, and change from baseline at Visit 3. Creatinine is collected as a safety laboratory parameter at all visits as described in Section 2.6.3, and will thus be summarized as part of safety laboratory. In addition NT-proBNP will be analysed by an ANCOVA according to description under secondary endpoints (Section 2.5.1). A shift table corresponding to those for safety lab will be provided.

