# 5 Appendix

# 5.1 Imputation rules

If the visit 3 assessment for the primary endpoint is missing for a subject then this will be imputed using a monotone regression approach including treatment and stratification as class variables. One hundred imputations will be done. Each replication of the data, including the imputed missing values, will then be analyzed using the ANCOVA used in the primary analysis, and estimates will be pooled using proc MIANALYZE SAS®.

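### The planned multiple imputation of cardiac efficiency repeats the ANCOVA's own terms and leaves observed visit 3 data unused, so it only returns the complete-case result

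*SAP*

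**What the plan says.** **Who is in the FAS.** SAP 2.2 requires a dose of randomised treatment and that subjects "have at least one post-baseline assessment of any efficacy endpoints".

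**When efficacy is measured.** The protocol synopsis (Methodology) says that the "PET-scan and echocardiography, will be performed twice during the study", at baseline and at the last visit. SAP 2.10 has NT-proBNP drawn "to assess effects of interventions on hemodynamics before randomization and repeatedly on visit 3". SAP 2.5.1 defines the blood pressure endpoint as "Systemic BP, evaluated in relation to PET and Echocardiography". SVR, coronary resistance and k_mono come from the same imaging sessions.

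**The endpoint.** SAP 2.4.1 gives "Myocardial efficiency = ((SBP x SV x HR)/LV mass)/Kmono", and defines SBP as the value taken during PET. Loss of any one component makes the whole value missing.

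**The imputation.** SAP 2.4.4: "The missing data will be imputed based on the factors (treatment and stratification) and baseline as covariate as applied in the ANCOVA". SAP 5.1: "If the visit 3 assessment for the primary endpoint is missing for a subject then this will be imputed using a monotone regression approach", with treatment and stratification as class variables and 100 imputations. Section 5.1 names neither baseline nor any visit 3 variable. The primary ANCOVA (SAP 2.4.2) has treatment, stratification and baseline efficiency.

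**The concern.** Together, these rules determine who is imputed. A subject who leaves before visit 3 has no post-baseline efficacy value, is outside the FAS and is never imputed. A subject who is imputed came to visit 3 and has part of the data: a PET without a usable echocardiogram, an echocardiogram without a usable PET, or at least NT-proBNP or imaging BP. Those values say something about the missing efficiency, yet the imputation model omits them.

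Multiple imputation improves on complete-case analysis only if it uses information that the analysis model lacks. Here it uses none. If loss of a scan is related to the subject's condition as seen in the visit 3 data that do exist, the treatment difference is biased, and the planned imputation leaves that bias in place although the data needed to reduce it are in the database.

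**Working it through.** **1. The plan's own figure.** Inputs from SAP 3: 15% change, CV 19.7%, two-sided alpha 0.05, power 80%. n per arm = 2 x [0.197 x (1.960 + 0.842) / 0.15]^2 = 27.08, against 27 stated. Power at 27 per arm is 79.9%. The figure is reproduced, so the same effect and spread are used below.

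**2. Why the two analyses agree.** Let X hold treatment, strata and baseline, and let b be the coefficients fitted to subjects with an observed outcome. Each imputed value is X(b + parameter draw) + residual draw. Averaged over imputations, the imputed points lie on the fitted surface Xb, and adding points on a fitted surface does not move a least-squares fit. The pooled estimate is therefore b plus noise of size sqrt(B/100), where B is the between-imputation variance. Imputing the visit 3 value or the change makes no difference, because baseline is in the model. This holds whatever the assumptions below.

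**3. Simulation.** From the documents: 30 per arm, effect 0.15, residual SD 0.197, 100 imputations. Assumed, not in the documents: three binary strata, baseline mean 1 and SD 0.25, slope of change on baseline -0.4, one or three missing per arm, and one visit 3 auxiliary variable with residual correlation 0.3, 0.6 or 0.8. There were 400 trials per setting.

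Three per arm missing at random:

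| Correlation | Estimate: complete case / SAP 2.4.4 | SE: complete case | SE: SAP 2.4.4 | SE: auxiliary added | SE: 5.1 read literally (no baseline) |
|---|---|---|---|---|---|
| 0.3 | 0.1483 / 0.1484 | 0.0557 | 0.0560 | 0.0559 | 0.0606 |
| 0.6 | 0.1489 / 0.1489 | 0.0552 | 0.0554 | 0.0544 | 0.0600 |
| 0.8 | 0.1471 / 0.1471 | 0.0553 | 0.0555 | 0.0535 | 0.0602 |

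- Within a trial, the SD of (SAP 2.4.4 minus complete case) is 0.0018, equal to sqrt(B/100) = 0.0018. Nothing but Monte Carlo noise separates them.
- Gain from the auxiliary: (0.0560 - 0.0559)/0.0560 = 0.2%; (0.0554 - 0.0544)/0.0554 = 1.8%; (0.0555 - 0.0535)/0.0555 = 3.6%. A second simulation, which added the observed component itself, gave 0.4-5%.
- Section 5.1 without baseline raises the SE by about 8% (for example 0.0600/0.0554 = 1.083) under the assumed baseline slope.

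One per arm missing at random: the SE under SAP 2.4.4 is 0.0537, 0.0540 and 0.0536 at the three correlations. With the auxiliary it is 0.0536, 0.0537 and 0.0529, a gain of 0.2%, 0.6% and 1.3%.

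**4. If loss depends on the visit 3 variable.** Suppose that in the treated arm the three missing subjects are those with the lowest auxiliary values (with some noise added), and in the control arm they are random. The true effect is 0.15.

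| Correlation | Complete case | SAP 2.4.4 | Auxiliary added |
|---|---|---|---|
| 0.6 | 0.1686 | 0.1685 | 0.1492 |
| 0.8 | 0.1769 | 0.1770 | 0.1508 |

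Complete case and planned imputation share the bias: 0.1685 - 0.15 = 0.0185 and 0.1770 - 0.15 = 0.0270, about a third and a half of one standard error. The auxiliary removes it.

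**The case against.** The strongest reply is that the planned step is redundant, not harmful. Complete-case ANCOVA is valid if missingness depends only on treatment, strata and baseline, and imputation on the same terms adds no bias to it. SAP 2.4.3 also expects very few withdrawals. This stands, and it limits the weight of the point. A failed scan in a subject who attends visit 3 is not a withdrawal, but the documents give no rate for it.

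The FAS argument also depends on how systemic BP is read. Protocol 3.2 and 9.2.6 and SAP 1.2.2 list it without qualification, and Protocol 8.3.2 says "BP and HR will be measured in a seated position after at least 5 min rest at all site visits for safety assessment". If that seated reading counted as an efficacy endpoint, an early withdrawal could enter the FAS with no visit 3 data, and auxiliary variables would not help. SAP 2.5.1 and the SAP table list tie the endpoint to imaging, but SAP 2.2 should say so.

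A reader might infer more than the documents support:

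- **That a material bias is to be expected.** The three-per-arm count equals 30 - 27, but that margin is for dropouts, most of whom would be outside the FAS. Selective loss in one arm is an artificial mechanism that no section suggests. In the second simulation, a deterministic worst-three-treated rule gave an overstatement of 1.4-3.4 points on a true 15, which is an illustrative extreme.
- **That half of the ratio is observed whenever one scan is lost.** SBP in the formula is the value during PET. Without a PET session both k_mono and SBP are missing, so work per gram is not observed. The SAP addendum computes LV work with the echocardiography SBP, which is a different quantity.
- **That the SAP uses this imputation to justify its treatment-policy reading.** Section 2.4.4 claims no such role. Section 2.4.6 attaches the ITT aim to the FAS, and 2.4.3 rests the reading on few withdrawals.
- **That an unreadable baseline scan would remove subjects from the primary analysis.** Section 5.1 speaks only of visit 3, but 2.4.4 covers any missing response, and nothing in the documents suggests that such losses occur.
- **That the visit 3 data are thrown away.** Many are analysed as endpoints in their own right. They are unused only in imputing the primary value.

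**Conclusion.** The point holds as a minor one. With systemic BP read as imaging-session BP, every FAS subject whose visit 3 efficiency is missing has another visit 3 efficacy measurement, and the imputation in SAP 2.4.4 does not use it. The planned imputation equals complete-case ANCOVA up to Monte Carlo noise, with an SE about 0.5% larger at three missing per arm. That equality follows from the method and needs no assumption about correlations or counts.

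The practical size does rest on assumptions. It is nil with no missing values. It is an SE reduction of about 0-5% with three per arm missing at random, and at most about 1% with one. Bias is removed only if scan loss depends on the observed visit 3 values. Section 5.1 as worded omits baseline and should be reconciled with 2.4.4 in any case.

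**What to change.** 1. In SAP 2.2, state that systemic BP counts towards FAS membership only when measured with PET or echocardiography.
2. Align SAP 2.4.4 and 5.1 so that baseline efficiency is in the imputation model.
3. Add observed visit 3 measurements as auxiliary variables: log k_mono, SV, LV mass, HR, and SBP at PET and at echocardiography, with EF or NT-proBNP where these are all that exists. Use fully conditional specification if the pattern is not monotone. Keep the set small for about 60 subjects and fix it before unblinding.
4. Where PET is missing, either impute SBP during PET and k_mono together, with echocardiography SBP as a predictor, or impute efficiency directly with the auxiliaries. Do not treat work per gram as observed.
5. Report the number of imputed values by arm, and the complete-case ANCOVA alongside.

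The cost is SAP wording and a few lines of SAS, with no new data. The downside is a few more predictors in a small imputation model.
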